2.2.1 Study Population

The study population will consist of approximately 144 subjects (36 per treatment group) between the ages of 18 and 75 years who are planning to undergo an elective unilateral BUNX and otherwise meet eligibility criteria (as described in the protocol Sections 10.1 and 10.2) may be considered for enrollment into the study.

2.2.2 Treatment Regimens

Study Material

The proposed doses of CA-008 to be evaluated in this study are:

- CA-008, 0.7 mg in 14mL of saline (0.05 mg/mL)
- CA-008, 2.1 mg in 14mL of saline (0.15 mg/mL)
- CA-008, 4.2 mg in 14mL of saline (0.30 mg/mL)

Comparator Group

- The placebo will use the same 14mL volume.

2.2.3 Treatment Group Assignments or Randomization

The study will be conducted in a randomized, double-blinded and placebo-controlled manner. The study includes 4 treatment groups (3 active and 1 placebo group). Subjects who meet the enrollment criteria will be randomly allocated in a 1:1:1:1 ratio to receive either active drug or placebo. Randomization will be accomplished manually on the day of surgery.

Subjects who have provided written informed consent will be assigned a unique number in the screening process. This number will be used to identify the subject throughout the study. Prior to randomization, subjects must meet all inclusion and not meet any exclusion criteria (as described in Sections 10.1 and 10.2). Once any subject number or randomization number is assigned, it cannot be reassigned to any other subject.

2.2.4 Sample Size Determination

In the previously completed Phase 1 ascending dose safety study in bunionectomy (CA-008 vs. placebo), the mean difference between CA-008 (all dose groups combined) and placebo for the area under the curve (AUC) from 24 to 96 hours was -120. The standard deviation (SD) estimates for the six treatment arms in this study ranged from 70 to 190 with a median SD of 108. For the primary endpoint (AUC₀ to 96h), the true treatment difference between the 4.2 mg CA-008 group and the placebo group is assumed to be equal to -100 and the assumed true SD is equal to 130. For these assumptions, and based on the use of a two-sided, two-sample comparison of means at the alpha=0.05 level of significance, a sample size of 36 subjects per arm will provide 90% power. Thus, the target sample size is 144 subjects.

3 GENERAL ANALYSIS AND REPORTING CONVENTIONS

This section discusses general policies to be employed in the analysis and reporting of the data from the study. Departures from these general policies may be provided in the specific detailed sections of this SAP. When this situation occurs, the rules set forth in the specific section take precedence over the general policies.

Each active dose will be presented separately in summaries and analyses as appropriate.

All continuous study assessments will be summarized by treatment and time point (as applicable) using the descriptive statistics n, mean, SD, median, and range (minimum, and maximum). All of the categorical study assessments will be summarized by treatment and time point (as applicable) using frequency counts and rates of occurrence (%). Changes from baseline for continuous outcomes will be presented as their corresponding continuous measures for post-baseline visits. All study data will be listed by dose, subject, and time point (as applicable).

No preliminary rounding will be performed; rounding will only occur after the analysis. To round, consider the digit to the right of the last significant digit: if <5, then round down; if ≥5, then round

up. Means and medians will be presented with one more decimal place than the precision of the data. Standard deviations will be presented with two more decimal places than the precision of the data. Percentages will be presented with one decimal place. A percentage of 100% will be reported as 100%. Minimums and maximums will be presented with the same precision as the original data.

All analyses will be performed using the SAS System® version 9.3 or higher. The domain (Study data tabulation Model [SDTM]) and analysis (Analysis Data Model [ADaM]) data sets will be taken as input to the SAS programs that generate the report-ready tables, figures and listings. The submission ready SDTM and ADaM data sets will be provided to the sponsor along with display deliveries.

The following conventions will be used throughout the study analysis:

- Time 0 (T0) is the time of completion of study drug administration.
- Day of surgery is defined as Day 0 (D0).
- Assessment visit times are defined by D0 and/or T0.
- Baseline value is defined as the last valid measurement prior to the dosing of study treatment.
- Change from baseline is defined as post-baseline value minus baseline value.
- Duration of an AE will be computed in days for AEs lasting longer than 24 hours, and as hours for AEs lasting less than 24 hours. Duration in hours will be calculated as the stop date/time of the event minus the start date/time. Duration in days will be calculated by using stop date minus the start date + 1 if AE occurs on or after taking study medication. If AE occurs prior to the study medication, then the duration will be calculated by using stop date minus the start date; If reported as ongoing at the time of database lock, the duration will be calculated using the date of the last visit or the last date of any AE for the subject in the database, whichever is later. Missing dates will be imputed as described in Table 8-1.
- The date/time of early termination will be the date/time that the subject confirms they no longer want to participate in the study, regardless of whether they decide to withdraw from all or only some study procedures and regardless of if they return for to the site for assessment of wound healing.
- The number of days in the study is computed as: [Date of study completion or withdrawal minus the date of study drug administration] + 1.
- If duplicate values are obtained at a given visit (e.g., repeated vital sign measurements), the last value will be used unless it is noted that the measurement was in error for that value. Values that compromise interpretation will not be used in summaries (e.g., values that were obtained post-dose will not be summarized as pre-dose values).

4 SUBJECT POPULATIONS

4.1 Analysis Populations

Six analysis populations are defined as follows:

- **Intent-to-treat (ITT)** population: all subjects who are randomized. Subjects will be analyzed according to the treatment they were randomized to.
- **Modified intent-to-treat (mITT)** population: all subjects who receive a full dose of study treatment and complete the first 3 pain assessments (through T2h). Subjects will be analyzed according to the treatment they were randomized to.
- **In patient study completer (Inpatient CP)**: all subjects who receive a full dose of study treatment and complete the inpatient assessment period (through T96h). Subjects will be analyzed according to the treatment they were randomized to.
- **Study Completers (CP)**: all subjects who receive a full dose of study treatment and complete the entire study period through D29±2/W4. Subjects will be analyzed according to the treatment they were randomized to.
- **Safety** Population will include all randomized subjects who received any amount of study drug. subjects will be analyzed by treatment group according to the actual treatment received, i.e., “as treated”.
- **Pharmacokinetic (PK)** population: All randomized participants who received a full dose of study drug and complete all PK assessments through the first 6 hours (T6h) time point. Note, subjects who fail to complete these PK assessments will be replaced.

Analysis populations will be determined before study unblinding.

The primary and secondary efficacy analyses will be performed using mITT population. Efficacy analyses will also be carried out using ITT, Inpatient CP and/or CP populations for selected endpoints as appropriate. Baseline characteristics will be summarized using ITT population and safety endpoints will be summarized using Safety population. PK summaries will be presented using the PK population.

4.2 Disposition of Subjects

All subjects and the populations for which they qualify will be listed. Subjects who are screened and who fail screening or withdraw consent prior to randomization or are randomized but not treated will be listed and summarized in the disposition summary table. Subjects who are randomized, subject inclusion into each study population, subjects who are treated, subjects who complete follow-up as well as subjects who withdraw early from the study and the reason for withdrawal will be summarized by treatment group and overall in the subject disposition summary table.

4.3 Protocol Deviations

Deviations are categorized as informed consent procedures, inclusion/exclusion criteria, study medication, prohibited medications, study procedures, study drug assignment/treatment, visit or

assessment time window, missed visit or assessment and/or other. All protocol deviations will be captured on case report forms (CRFs) and/or documented in site specific logs throughout the study. Deviations will be categorized and classified as major or minor by the project team and the medical monitor after database lock but before unbinding and will be discussed in the CSR. The number of subjects with protocol deviations, both minor and major, will be presented in a data listing and will be summarized by type of deviation and major/minor classification for the ITT population.

5 DEMOGRAPHIC AND OTHER BASELINE CHARACTERISTICS

5.1 Demographics and Baseline Characteristics

Demographic variables include age, sex, race, and ethnicity. Baseline characteristics include American Society of Anesthesiologists (ASA) physical status, target foot (Left/ Right), height, weight (kg), and body mass index (BMI; kg/m²). Demographics and baseline characteristics will be presented in a by-subject listing and summarized overall and by treatment group using ITT population.

5.2 Medical/Surgical History

The complete medical and surgical history will include histories of acute, chronic, or infectious disease; surgical or oncologic histories; and any reported conditions affecting major body systems. Subject's medical history will be evaluated by an Investigator for clinical significance.

Medical and Surgical history, as collected at screening, will be coded using the Medical Dictionary for Regulatory Activities (MedDRA) version 21.0 to determine system organ class (SOC) and preferred term (PT). Medical histories will be presented in a by-subject listing.

Any events that occur prior to the study procedure will be categorized as medical history.

5.3 Prior and Concomitant Medications

Prior medications/therapies are those that stop prior to the start of the study drug administration. Any medication/therapy that stops at or after this time or with missing stop dates is considered concomitant medication/therapy.

Prior and concomitant medications are collected for the 30 days prior to screening and throughout the study. Prior and concomitant medications will be coded using World Health Organization Drug Dictionary Anatomical Therapeutic Chemical (WHO/ATC) classification index version March 1, 2018. The number and percentage of subjects who take concomitant medications will be summarized by drug class and preferred term, overall and by treatment group, for the safety population.

All medications and non-medical therapies captured in CRFs will appear in data listings.

6 MEASUREMENTS OF TREATMENT EXPOSURE and COMPLIANCE

CONFIDENTIAL

Because study medication is administered as a single dose at the study center by trained study personnel, compliance with respect to study medication will not be calculated. A listing of study drug administration and exposure data will be provided.

After completing the assessments through 96 hours after study medication administration, the diary for at-home use will be distributed to the subject to collect pain intensity (twice daily on NRS) and pain medication through Day 15. Compliance with home diary use will be evaluated based on post-discharge home diary records. Compliance for each subject will be based on the number of days the subject participated in the outpatient study period, defined as:

Compliance (%) =

$$\frac{(N \text{ of non-missing NRS recorded on Diary})}{(N \text{ of Expected NRS from Diary})} \times 100$$

Where the N of expected NRS records in the diary for each subject is calculated as 2 times the number of days the subject participated in the outpatient portion of the study. The number of days of participation will be calculated as the date of the Day 15 visit or the date of the last study visit (whichever is earlier) minus the date of discharge. NRS recorded prior to a rescue use will not be included in this calculation of compliance.

For example, Subject A was discharged on Day 4, if this subject discontinues the study on Day 13, then the expected N of NRS records on diary will be 18 (2 * (13-4)). Assuming Subject A had 10 NRS available from his/her diary, then compliance for this subject would be 55.6% ((10/18) *100). However, if subject A had discontinued the study on Day 10 (prior to Day 13), then the expected N of NRS for this subject would be 12 (2 * (10-4)) and compliance would be 83.3% ((10/12) *100). A summary of compliance will be provided overall and by treatment group.

Compliance with recording an NRS prior to rescue in the diary will be calculated as the number of NRS recorded prior to taking rescue medications divided by the number of rescue medication uses recorded.

7 EFFICACY EVALUATION

7.1 Handling of Dropouts or Missing Data

All efforts will be made to minimize missing data. These efforts will include the following:

- Subjects are required to consent to continuous data collection even after discontinuation of study medication;
- Data collection will continue after subjects take rescue medication.

With the procedures above, it is expected that missing data will be minimal. Missing at random is expected to be a reasonable assumption for this dose-escalation study.

For the endpoints of NRS (at rest and/or after ambulation) in this study, NRS values will be imputed in the following manner:

First, when rescue medication is used, any NRS measured at rest within the next 4 hours is considered invalid. Therefore, the last NRS prior to the use of any rescue medication will be used to impute subsequent NRS at rest scores for the subsequent protocol-specified time points for measurement of pain intensity through 4-hours after the time of the dosing of the rescue medication. Note: if a pre-rescue NRS assessment occurs at the same time as a scheduled assessment, the schedule NRS will be assumed to happen first, and then the pre-rescue NRS will be assumed to occur. If an NRS assessment occurs at the same time as the time of taking a rescue medication, the NRS will be assumed to be a Pre-rescue medication result. If the NRS time is the same as 4 hours after taking the rescue medication (end of imputation period), then NRS will be considered as occurring before the 4 hours assessment and will be imputed. For example, if a rescue dose is taken at 1pm, all protocol-scheduled NRS will be imputed with the appropriate NRS value up to and including through 5pm. If multiple doses of rescue medication are taken within a 4-hour period, the pre-rescue NRS for the first rescue use will be carried forward continuously until 4 hours past the last use of rescue falling within the continuous window. For example, if rescue is used at Hour 2.3 and Hour 5.1, the pre-rescue NRS at Hour 2.3 will be carried forward till Hour 9.1 (5.1 +4). NRS scores taken after ambulation will be based on reported values and the pre-rescue 4-hour imputation rule will not be used. The scores after ambulation are collected every 12 hours and no ambulation NRS score is collected prior to taking rescue medication.

For subjects who take prohibited medication, NRS results collected after taking the prohibited medication will not be used for AUC calculations but will be imputed according to the methods used for discontinued subjects.

Intermittent missing pain scores at rest or after ambulation (due to subject sleeping, etc.) will not be imputed, and AUC will be calculated based on non-missing values. For subjects who drop out of the study or take prohibited medication prior to Day 15, scheduled assessments will first be imputed using the worst prior pain score carried forward (WOCF).

Two sensitivity analyses will be performed to evaluate the robust of the primary result:

- 1) AUC will be calculated where assessments after drop out will be imputed using LOCF, using the last scheduled non missing pain score prior to drop out.
- 2) AUC will be calculated where assessments after dropping out will be imputed using the median score from the remainder of subjects in the group continuing in the study.

For secondary continuous efficacy endpoints, similar methods as the primary analysis will be used. For categorical endpoints, when assessments are imputed for data after a subject discontinues from the study, a WOCF method will be used.

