2.2 Overall Study Design and Plan

This is a Phase 2, multi-center, randomized, double-blind, placebo-controlled, parallel design study evaluating a single dose of one of three CA-008 dose groups vs. placebo injected during an elective BUNX under light to moderate sedation supplemented by a Mayo block with bupivacaine hydrochloride (HCl) and a multimodal analgesia regimen, including ketorolac and acetaminophen, and access to rescue medication (oxycodone).

During the screening phase, subjects requiring bunionectomy between the ages of 18 and 75 years, inclusive, will be screened at the study site in the United States within 45 days of surgery/study treatment administration. Subjects who meet the selection criteria and are eligible to participate in the study will be required to return to the study center for surgery.

The study will be conducted in two parts:

- Inpatient period which continues to 96h after completion of study treatment injection (T0) or T96h.
- Outpatient period which begins on discharge from the inpatient unit through various follow up visits to D29±2 (W4) after surgery, or if necessary for ongoing safety assessments, to D36±2 (W5).

Subjects will be undergoing unilateral transpositional first metatarsal osteotomy for the correction of hallux valgus deformity (bunionectomy or BUNX). The surgery is to be performed under light to moderate sedation anesthesia (what constitutes this level of sedation and the additional anesthetic medications used per discretion of the anesthesiologist). In accordance with standard of care, light to moderate sedation will be supplemented with a Mayo block to produce surgical anesthesia and postoperative analgesia. After administering light to moderate sedation, but prior to surgery, perform a Mayo block by infiltrating 0.5% bupivacaine hydrochloride (up to 30 mL total volume, 150 mg) at least 3 cm proximal to the “surgical site”. The Mayo block should be performed at 15-30 minutes prior to study treatment dosing. “Surgical site” is defined as the area extending approximately 2-3 cm in all directions (lateral/medial/proximal/distal) from the incision site and surrounding tissues which may be affected by the infiltration of study treatment.

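### SAP 7.1 assumes missing at random, but no planned analysis rests on it, and the arm-median sensitivity analysis has too small a standard error and can bias the contrast

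*SAP*

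**What the plan says.** SAP 7.1 gives the assumption in one sentence: "Missing at random is expected to be a reasonable assumption for this dose-escalation study". It also says: "With the procedures above, it is expected that missing data will be minimal". Neither document gives an expected dropout rate.

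For subjects who drop out before Day 15, SAP 7.1 fills the remaining scheduled scores with the worst prior score (WOCF); this is the primary analysis. Two sensitivity analyses change only that fill. The first carries the last score forward (LOCF). In the second, "AUC will be calculated where assessments after dropping out will be imputed using the median score from the remainder of subjects in the group". Scores recorded after prohibited medication are discarded and handled by the same methods. SAP 7.5.2 analyses the resulting AUC by one-factor ANOVA, as if every filled value had been observed.

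The design is described in SAP 2.2: "This is a Phase 2, multi-center, randomized, double-blind, placebo-controlled, parallel design study evaluating a single dose of one of three CA-008 dose groups". Under SAP 2.2.3, subjects are "randomly allocated in a 1:1:1:1 ratio to receive either active drug or placebo". The dose-escalation label in 7.1 therefore does not fit this trial.

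**The concern.** Under MAR, the chance of leaving may depend on pain already recorded. An analysis valid under MAR must use that record to predict the missing scores and must carry the uncertainty of the prediction. WOCF and LOCF use the record, but only by freezing one score, and they carry no uncertainty. The median rule does not use the subject's record at all after dropout. It treats a leaver as a typical stayer, which in general requires leavers and stayers in an arm to be alike.

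The SAP gives reason to doubt that they are alike: section 7.5.7 assumes that dropout for an adverse event or lack of efficacy is pain related. The prohibited-medication rule widens the exposure. Protocol 9.1.3 bars further NSAIDs and acetaminophen through T96h, so a subject who takes one for poorly controlled pain also moves into imputation.

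At stake is the value of the robustness check. An analysis with a standard error that is too small can reassure falsely, and a shifted contrast can mislead in either direction.

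**Working it through.** **Inputs.** 36 per arm, difference -100, SD 130, two-sided 0.05 (SAP 2.2.4); one-factor ANOVA (SAP 7.5.2); resting scores at 10 times to T24h and then every 4 hours to T96h, 10 + 18 = 28 scheduled scores (SAP 7.5.1). Dropout rates and mechanisms are assumed.

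**1. The plan's own figure.** n = 2 × (1.960 + 1.282)² × 130² / 100² = 35.5, so 36 per arm. Power is 0.904 by the normal formula and 0.896 by the two-sample t. The sample size reproduces and is not in question. The complete-data SE is 130 × √(2/36) = 30.6.

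**2. Assumption behind each planned analysis.**
- WOCF: the leaver's pain stays at its worst prior value.
- LOCF: the leaver's pain stays at its last value.
- Arm median: the leaver's later pain is that of the stayers.
- Completer analyses (Tables 14.2.2.1 to 14.2.2.4): inpatient dropouts are excluded by definition (SAP 4.1), so these cannot test how such dropouts are handled.

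No multiple imputation or mixed model is planned.

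**3. Bias of the median rule.** Suppose dropout occurs at T24h, so that 72 hours are filled. Let p be the dropout proportion in an arm and d the fill minus what the leavers would have scored. Then

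bias = 72 × (p_active × d_active - p_placebo × d_placebo).

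Simulations used 36 per arm, between-subject SD 1.3, within-subject SD 1.2, leaving weighted by early pain, and a true difference of about -98:

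| Who leaves | Placebo / 4.2 mg | Median-rule estimate |
|---|---|---|
| High-pain | 15% / 5% | -88 |
| High-pain | 5% / 15% | -108 to -109 |
| Low-pain | 15% / 5% | -109 |
| Low-pain | 5% / 15% | -88 |
| Random | same rates | -97 to -98 |
| Equal rates | 3, 5 or 10% each | bias within 0.3 |

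The shift of 10 implies d of size 10 / (72 × 0.10) = 1.4 NRS points. With d = -1.4 in both arms, the first row gives 72 × (-0.07 + 0.21) = +10.1, which agrees. For two leavers against one, the bias is 72 × 1.4 × (1/36) = 2.8, under a tenth of the SE.

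With dropout spread over 12 to 72h, a true difference of -100 and pain-driven leaving, the bias was about +5 at 11% placebo / 5% active and +10 at 25% / 12%. Equal rates do not guarantee safety if the pattern differs: with 11% in each arm, high-pain subjects leaving placebo and low-pain subjects leaving active, the bias was +17.

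**4. Standard error.** If a proportion p at random received a constant for the whole AUC, the estimated variance of the arm mean would shrink by about (1 - p) and its true variance would grow by about 1/(1 - p). The ratio of reported SE to actual SD would then be about 1 - p. Late dropout softens this; selective loss of extreme subjects worsens it. Simulated values:

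| Dropout, placebo / active | Timing | Mean SE | Actual SD | Ratio |
|---|---|---|---|---|
| 3% / 3%, random | 12 to 72h | 30.3 | 30.6 | 0.99 |
| 3% / 3%, random, no effect | 12 to 72h | 30.2 | 31.4 | 0.96 |
| 9% / 9%, random | 12 to 72h | 29.6 | 31.8 | 0.93 |
| 17% / 17%, random | 12 to 72h | 28.5 | 31.6 | 0.90 |
| 11% / 5%, pain-driven | 12 to 72h | 28.5 | 30.2 | 0.94 |
| 5 of 36 / 2 of 36, pain-driven | T24h | 26.9 | 30.5 | 0.88 |
| 15% / 5%, pain-driven | T24h | 26.8 | 31.5 | 0.85 |

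With 1,500 trials, Monte Carlo error on a ratio is about 1/√3000 = 0.02. One run with 3% strongly pain-driven dropout at T24h gave 0.92, the most adverse value at that rate. With no true effect and equal pain-driven dropout over 12 to 72h, the median analysis rejected in 6.4% of trials at 11% dropout and 9.2% at 24%, against a nominal 5%.

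**5. A MAR-based analysis in the same settings.** A likelihood estimator using each subject's own history (covariance taken as known) had bias within about 1.4 units, an SE ratio of 0.98 to 1.04 and coverage of 0.946 to 0.962 in the 12 to 72h scenarios. In the 5-against-2 scenario, multiple imputation from a summary of early scores gave -97 with SE 29.9. The truth there was -97, and the median rule gave about -88.

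**The case against.** The strongest reply is that little will be missing. There is one intraoperative dose and a 96-hour inpatient stay, and subjects who discontinue are asked to continue assessments through T96h. With one or two dropouts per arm the point is small. That stands, and it limits the size of the concern. A sensitivity analysis exists, however, for the case in which the expectation fails.

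Second, this is the second of two sensitivity analyses. The primary test uses WOCF, and the testing hierarchy in SAP 7.3 depends on that result alone. This also stands. A reader might infer that the primary conclusion is compromised; nothing here shows that.

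Third, scores before dropout remain in the AUC, so the subject's own pain is ignored only in the filled part. Correct.

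Fourth, a reader might infer that the median rule always biases the contrast under MAR, or that more dropout on CA-008 always overstates the effect. Neither holds. Bias vanished with random or balanced dropout, and its direction reversed when low-pain subjects left.

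Finally, the dose-escalation label might be read as affecting the analysis. It changes no calculation and is a wording error only.

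**Conclusion.** The point holds in a limited form. The SAP states MAR and plans no analysis valid under it. The median analysis understates its standard error: by about 1 to 5% at roughly 3% dropout (8% in one adverse run), by about 4 to 10% at 9 to 17% dropout spread over 12 to 72h, and by about 10 to 15% when roughly 10 to 15% of an arm leaves around T24h. It can shift the contrast by about 5 to 17 units on a true -100 at 11 to 15% dropout, if dropout depends on pain and differs between arms in rate or pattern. The sign depends on who leaves and from which arm.

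These sizes rest on assumed dropout rates and on normally distributed scores with flat means. Bounded or skewed scores would add a mean-versus-median difference not modelled here. The SAP also does not say whether the median is taken at each time point; the simulations took it that way. This is a worthwhile, low-cost improvement to a supporting analysis, with no consequence for the confirmatory test.

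**What to change.** Replace sensitivity analysis 2 in SAP 7.1, or add beside it, multiple imputation under MAR:
- Impute by arm from a short summary of each subject's own earlier scores, for example mean pain to date and last score. With 28 scheduled inpatient scores and 36 subjects per arm, a model using every score separately would be too large.
- Combine by Rubin's rules, with a stated seed. An equivalent mixed model would also serve.
- State that this is the analysis that rests on MAR. Update Table 14.2.1.5 and Figure 14.2.1.3.
- If the median analysis is kept, say whether the median is taken at each time point.
- Change dose-escalation to parallel-group.

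A control-based run, with active-arm dropouts imputed from placebo, is optional. Protocol 15.6.4 already allows further dropout-imputation sensitivity analyses and says that imputation methods will be documented in the SAP, so SAP text suffices. The cost is some programming, Monte Carlo error, a slightly wider interval and a method a little harder to explain.
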